3.4. Age

There is a 50% chance of observing a lesion in a 20- to 49-year-old in the training set, but a 90% chance of observing at least 2 lesions in patients age 50 to 64. There is a 75% chance of observing at least 3 lesions in patients age 50 to 64 in the training set (Table 3.4.2).

There is a 75% chance of observing a lesion in a 20- to 49-year-old in the validation set. There is a 90% chance of observing at least 4 lesions in patients age 50 to 64, and a 75% chance of observing at least 5 lesions in patients age 50 to 64 in the validation set (Table 3.4.3).

Table 3.4.1. Underlying data by age.²⁴

Group	% of positive NMSC diagnosis population
20-49	6.5%
50-64	22.9%
65+	69.8%

Table 3.4.2. Simulations for training set (N=20) by age.

Group	N sims	10 th Pctl	EV	Std Dev	Min	1 st Pctl	25 th Pctl	Median	75 th Pctl	90 th Pctl	99 th Pctl	Max
20-49	10,000	0	1.3	1.11	0	0	0	1	2	3	4	7
50-64	10,000	2	4.6	1.87	0	1	3	4	6	7	9	12
65+	10,000	11	13.9	2.05	7	9	13	14	15	17	18	20

Table 3.4.3. Simulations for validation set (N=30) by age.

Group	N sims	10 th Pctl	EV	Std Dev	Min	1 st Pctl	25 th Pctl	Median	75 th Pctl	90 th Pctl	99 th Pctl	Max
20-49	10,000	0	1.9	1.34	0	0	1	2	3	4	6	10
50-64	10,000	4	6.9	2.33	0	2	5	7	8	10	13	16
65+	10,000	18	20.9	2.53	11	15	19	21	23	24	26	30

3.5. Sex

The chance that both sexes are represented in the training set is close to 100%. The chance of obtaining samples for at least 7 patients for each sex is 90% (Table 3.5.2).

The chance that both sexes are represented in the validation set is close to 100%. The chance of obtaining samples for at least 11 patients for each sex is 90% (3.5.3).

Table 3.5.1. Underlying data by sex.²⁴

Group	% of positive NMSC diagnosis population
Female	50%
Male	50%

Table 3.5.2. Simulations for training set (N=20) by sex.

Group	N sims	10 th Pctl	EV	Std Dev	Min	1 st Pctl	25 th Pctl	Median	75 th Pctl	90 th Pctl	99 th Pctl	Max
Female	10,000	7	10.0	2.23	2	5	9	10	12	13	15	18
Male	10,000	7	10.0	2.23	2	5	8	10	11	13	15	18

Table 3.5.3. Simulations for Validation Set (N=30) by sex.

Group	N sims	10 th Pctl	EV	Std Dev	Min	1 st Pctl	25 th Pctl	Median	75 th Pctl	90 th Pctl	99 th Pctl	Max
Female	10,000	11	15.0	2.74	5	9	13	15	17	19	21	25
Male	10,000	11	15.0	2.74	5	9	13	15	17	19	21	25

Any reproduction in part or whole without the written permission of Enspectra Health, Inc. is prohibited.

Appendix C: Assignment of Subjects to Training and Validation Sets

1.1 Overview of Sample Assignment to the Training Set or Validation Set

1.1.1 Samples will be assigned to either the Training set or Validation Set using a pre-specified procedure designed to accomplish the following three objectives:

1.1.1.1 Ensure the Training and Validation sets are comparable across categories of interest (i.e., Conditions, Fitzpatrick Skin Type, Anatomical Region of Lesion, Age, and Sex), using a maximum Standard Mean Difference (SMD) <0.2 .

The maximum SMD was chosen to assess comparability because it is a widely accepted diagnostic measure of covariate balance in propensity score matched groups.¹ It can be applied in this setting to compare the frequency distributions of characteristics of interest between the Training and Validation sets. The use of a cut-off of 0.2 is based on Cohen's Effect² Size Index, and this threshold is a common choice for balance diagnostics in propensity score matching.

1.1.1.2 Minimize bias in assignment, and

1.1.1.3 Meet minimum enrollment targets for both the Training and Validation sets as specified in the study protocol.

1.1.2 To assign samples, 500 randomization assignment schedules will be generated. The first schedule that simultaneously meets the minimum enrollment targets for both the Training set and Validation set, and meets the requirement of a maximum Standard Mean Difference (SMD) <0.2 will be selected and used to assign samples to these sets.

¹ Austin PC. Balance diagnostics for comparing the distribution of baseline covariates between treatment groups in propensity-score matched samples. *Stat Med*. 2009;28(25):3083-3107. doi:10.1002/sim.3697

² Cohen J. *Statistical Power Analysis for the Behavioral Sciences* (2nd edn). Lawrence Erlbaum Associates Publishers: Hillsdale, NJ, 1988.

meeting pre-specified requirements. This schedule will be used to assign

The study protocol requires a minimum enrollment of (50) subjects, and assignment of 20 subjects to the Training Set and 30 subjects to the Validation Set. If more than 50 subjects are enrolled, excess subjects will be assigned to maintain the original ratio (40% of subjects assigned to the Training Set, 60% of subjects assigned to the Validation Set).

1.2.10 Validation of the Assignment Spreadsheet.

1.2.10.1 Prior to usage with real study data, the Assignment Spreadsheet will be tested and validated with simulated data. To generate a simulated data set, randomized categories will be assigned to hypothetical subjects using the probabilities expected in the population (Tables 1-5).

[REDACTED]

[REDACTED]

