10.1 Study Population

The target study population includes men and women 18 – 99 years old in the United States undergoing a routine skin biopsy. A maximum of 65 subjects may be enrolled at 2-5 sites (training set: N=20 subjects; validation set: N=30 subjects; Total N=50). Additional 15 subjects may be enrolled in the study in order to meet comparable distribution of samples as described in the tables below. Samples will be collected across a representative range of skin conditions, Fitzpatrick Skin Types, anatomical locations, ages and genders that are expected in actual

clinical usage (see Tables 1 - 5). Eligible subjects include those undergoing routine skin biopsies that meet the inclusion/exclusion criteria.

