*Sample ranges based on 10th (lower) and 90th (upper) percentiles from simulations (see Appendix A). Minimum value for the number of samples required in the study is the lower bound of the range (derived from 10th percentile). There is no maximum value for any sample type.

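### Are 500 random schedules enough to find a training/validation split that meets the Appendix C balance rule?

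*Combined protocol and SAP*

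**What the plan says.** Appendix C divides enrolled subjects between the training and validation sets by a pre-specified procedure. Under 1.1.2, "To assign samples, 500 randomization assignment schedules will be generated". The one used is "The first schedule that simultaneously meets the minimum enrollment targets for both the Training set and Validation set" and also keeps the maximum SMD below 0.2.

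Under 1.1.1.1 the SMD serves to "compare the frequency distributions of characteristics of interest between the Training and Validation sets". The characteristics are condition, Fitzpatrick type, lesion location, age and sex, which have 15 levels in Tables 1–5 of section 11.2. The footnote to those tables makes the lower bounds binding: "Minimum value for the number of samples required in the study is the lower bound of the range".

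The split is 20/30 at 50 subjects. Beyond that, "If more than 50 subjects are enrolled, excess subjects will be assigned to maintain the original ratio", which is 40/60. Section 10.1 adds: "Additional 15 subjects may be enrolled in the study in order to meet comparable distribution of samples". Under 1.2.10.1 the spreadsheet is validated, before real data are used, on hypothetical subjects drawn from the Table 1–5 probabilities.

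Most of section 1.2, which holds the step-by-step procedure, is not visible.

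**The concern.** The visible text neither derives the figure of 500 nor says how often one of 500 schedules would qualify. A limit of 0.2 on every level of five characteristics is tight for sets of 20 and 30. Moving one subject of a given level from one set to the other, in exchange for a subject of another level, changes the difference in proportions by 1/20 + 1/30 = 0.083.

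If the search usually came back empty, the next step would decide the assignment. An improvised step would weaken the appendix's aim of limiting bias. Repeating the search as the 15 extra subjects arrive would spend subjects on what is partly a computing problem. A level with a single subject might also make the threshold unreachable, and the zero minima for limb lesions and for age 20–49 permit that.

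**Working it through.** **Inputs.** Subgroup proportions and minima come from Tables 1–5; age sums to 99.2% and was rescaled to 100%. Set sizes (20/30, or 26/39 at 65 subjects), the 0.2 threshold and the 500 schedules come from Appendix C. The assumptions are that the characteristics are independent (Appendix A models each one separately) and that schedules are unrestricted random 40/60 splits.

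**The plan's own figures.** The Table 1–5 minima reproduce as binomial 10th percentiles in 29 of 30 cells. The exception is Fitzpatrick Type I in the validation set (stated 1, computed 2). There P(X ≤ 1) = 0.099 for n = 30 and p = 0.124, so it is a borderline case within simulation error.

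**Level SMD.** With p_T and p_V the proportions in the two sets, SMD = |p_T − p_V| / √{[p_T(1−p_T) + p_V(1−p_V)]/2}.

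*How tight the limit is.* Take 25 women among 50 subjects. A 10/15 split gives SMD 0. An 11/14 split gives 0.0833/0.498 = 0.17, which passes. A 12/13 split gives 0.1667/0.493 = 0.34, which fails. All 15 levels must pass together.

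*A level with one subject:*
- 20/30, subject in training: 0.05/√(0.05 × 0.95/2) = 0.324
- 20/30, subject in validation: 0.0333/√(0.0333 × 0.9667/2) = 0.263
- 26/39: 0.283 and 0.229 in the same way

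All four exceed 0.2, so a level-wise rule cannot pass such a pool under any split. The same holds for the multi-category (Mahalanobis) form, which was never below its largest level SMD in 40,000 schedules. Some level has exactly one subject in about 24% of pools at 50 subjects and 10% at 65.

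**Simulation.** Pools were drawn from the Table 1–5 proportions. A pool is workable if every level total is at least the sum of its two minima; about 21% of pools at 50 subjects are not, and about 1% at 65. Each workable pool was split 500 times. The table gives the share of workable pools with at least one qualifying schedule; ranges are over repeated independent runs.

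| SMD form | 50 subjects | 65 subjects |
|---|---|---|
| Maximum over levels | 18–21% | 53–57% |
| Multi-category | 8.5–10% | about 35% |
| Ordinal for skin type and age, level-wise for the rest | 67–68% | 94% |
| Averaged over levels within a characteristic, then maximum | 97–98% | over 99% |
| Ordinal for all five | 98–99% | over 99% |

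As a check, the level-wise pass rate per schedule at 50 subjects averages about 0.0005, and 1 − (1 − 0.0005)^500 = 0.22. That is close to the simulated share, which averages over pools with different rates.

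**How far other readings move this.** Stratifying schedules by condition raises the level-wise share at 50 subjects to roughly 50%. If the rule is retried after each added subject up to 65, it succeeds in about 90% (level-wise) or 87% (multi-category) of all pools, using on average 4.7 or 6.9 of the 15 extra subjects.

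**The case for a change.** The strongest case for a change is that the unfavourable readings are natural ones. A maximum SMD applied to frequency distributions suggests a level-wise or multi-category form, whereas a full ordinal score would have to be imposed on condition and location, which are nominal. The one-subject result needs no simulation: it follows from the plan's own threshold, set sizes and minima. Drawing more schedules costs almost nothing and uses no subjects.

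The arithmetic stands, but the inference to a defect does not. The result needs three things together: the SMD form, unrestricted splits and a single attempt at fixed enrolment. The first two would be settled in the hidden part of 1.2. The third sits badly with section 10.1, which allows enrolment past 50 for the sake of comparability; about a fifth of pools at 50 subjects need it anyway to meet the minima.

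The available remedies are not clear gains either. With 20,000 schedules the level-wise share at 50 subjects rises only to about 75%, because one-subject pools still fail. Going further means exempting or merging those levels, or accepting an SMD above 0.2. Each of these relaxes the plan's own criterion and is a matter of judgement.

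**Conclusion.** No change is called for. On a level-wise or multi-category SMD with unrestricted splits and one attempt, 500 schedules would usually be too few at 50 subjects (about 20% or 9% success). On an averaged or fully ordinal SMD they are ample. The visible text does not decide between these, and section 1.2 may.

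Whichever applies, little depends on it. Section 13.2.4 estimates blinded-reader accuracy from the validation set alone, and no endpoint, interval or decision rule uses the training/validation SMD. Any effect on the primary result is indirect, through how well the training set prepares the readers. The 1.2.10.1 test uses the same proportions as the simulation here and would reveal an empty search before real data are touched. The sensible response would then be to generate further schedules under the same criteria.

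The percentages assume independent characteristics and recruitment at the Table 1–5 rates. The one-subject result does not depend on either assumption.
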